4. STUDY POPULATION

It is expected that data will be collected from approximately 1000 patients at approximately 200 sites (primary care centres) in Spain. Sites will be selected in a way that reflects routine clinical practice for COPD in order to ensure the representativeness of the population with COPD. The inclusion of 5 patients per investigator has been planned.

A record will be kept of all patients included in the study (i.e., who have given their informed consent) in the investigating site's file, irrespective of whether they have been treated or not.

4.1. SELECTION CRITERIA

Patients who meet all the criteria listed below may be included:

4.1.1. Inclusion criteria

1. Written informed consent prior to participation
2. Female and male patients ≥ 40 years of age
3. Patients diagnosed with COPD and requiring long-acting dual bronchodilation (LAMA + LABA) treatment according to approved Spiolto® Respimat® SmPC and COPD GOLD guideline recommendation

4.1.2. Exclusion criteria

1. Patients with contraindications according to Spiolto® Respimat® SmPC
2. Patients who have been treated with a LABA/LAMA combination (free and fixed dose) in the previous 6 months
3. Patients continuing LABA-iCS treatment should not be additionally treated with Spiolto® Respimat® in order to avoid a double dosing of long-acting beta-agonists
4. Patients for whom further follow-up is not possible at the enrolling site during the planned study period of approx. 6 weeks
5. Pregnancy and lactation
6. Patients currently listed for lung transplantation
7. Current participation in any clinical trial or any other non-interventional study of a

drug or device

4.2. RATIONALE FOR SAMPLE SIZE

In a previous study, 205.426 (clinicaltrials.gov NCT 00699699: "Assessment of Physical Activity (PF10 Sub Domain of SF-36 Activity Score) and Tolerability in COPD Patients During Treatment With Spiriva® Respimat®"), with more than 1000 patients treated with Spiriva® Respimat®, therapeutic success (i.e., 10-point increase in the PF-10 score between visit 1 and visit 2) was achieved in 61% of patients.

In this study, a lower therapeutic success rate is expected, as patients may already be on maintenance treatment at the start. Assuming a therapeutic success rate of 50% and 900 patients, the 95% confidence interval for the therapeutic success rate would be between 46.7% (lower limit) and 53.3% (upper limit) (level of accuracy of $\pm 3.3\%$), basing the calculations on a normal approximation to the binomial distribution.

Taking into account a possible drop-out rate of 10%, the sample size is adjusted to 1000 patients.

Calculations were made using the PASS software package, version 2011.

5. METHODS

5.1. DATA PROCESSING

The data management process detailed in the Data Management Plan (DMP) for studies conducted only in electronic format, includes the coding and the definition of the filters for the validation of data during the tabulation of the data or once in tabulated form.

5.2. DATA ANALYSIS AND STATISTICAL TESTS

5.2.1. Important protocol violations

The next table defines the different categories of important protocol violations (PVs). The final column describes which PVs will be used to exclude subjects from the different patient analysis sets:

Description	Requirements	Excluded from
Entrance criteria not met		
Inclusion criterion 1 (Written informed consent prior to participation)	not met as specified in the protocol	None
Inclusion criterion 2 (Female and male patients \geq 40 years of age)	not met as specified in the protocol	None
Inclusion criterion 3 (Patients diagnosed with COPD and requiring long-acting dual bronchodilation (LAMA + LABA) treatment according to approved Spiolto® Respimat® SmPC and COPD GOLD guideline recommendation)	not met as specified in the protocol	None
Exclusion criterion 1 (Patients with contraindications according to Spiolto® Respimat® SmPC)	met as specified in the protocol	None
Exclusion criterion 2 (Patients who have been treated with a LABA/LAMA combination (free and fixed dose) in the previous 6 months)	met as specified in the protocol	None
Exclusion criterion 3 (Patients continuing LABA-ICS treatment should not be additionally treated with Spiolto® Respimat® in order to avoid a double dosing of long-acting beta-agonists)	met as specified in the protocol	None
Exclusion criterion 4 (Patients for whom further follow-up is not possible at the enrolling site during the planned study period of approx. 6 weeks)	met as specified in the protocol	None
Exclusion criterion 5 (Pregnancy and lactation)	met as specified in the protocol	None
Exclusion criterion 6 (Patients currently listed for lung transplantation)	met as specified in the protocol	None
Exclusion criterion 7 (Current participation in any clinical trial or any other non-interventional study of a drug or device)	met as specified in the protocol	None
Informed consent		
Informed consent not available/not done	Inclusion criterion not met as specified in the protocol or informed consent date missing	All

5.2.2. Population for analysis

Three populations will be used for the analysis:

1. **All screened patients:** defined as all recruited patients with informed consent and date of registration.
2. **Treated Set (TS):** All screened patients with at least one documented administration of Spiolto® Respimat®. This population will be used in the safety endpoints, demographics/baseline, and other summary tables.
3. **Full Analysis Set (FAS):** All screened patients with at least one documented administration of Spiolto® Respimat® and available PF-10 score at visit 1 and visit 2. This population will be used in the primary and secondary tables,

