9.7 DATA ANALYSIS

9.7.1 Main analysis

In this non-interventional study, cross-sectional data at study baseline and longitudinal follow-up data over 6 weeks will be collected for patients with chronic obstructive pulmonary disease (COPD) requiring long-acting dual bronchodilation in routine clinical practice.

Baseline data will be described using a cross-sectional approach. Data from the longitudinal follow-up will be summarized descriptively. Due to the nature of this non-interventional study, there is no (confirmatory) hypothesis testing foreseen in a strict statistical sense. Analyses are descriptive in nature and confidence intervals and p-values from statistical models are used for exploratory purposes. No adjustments for multiple testing are made in the evaluation of statistical significance. Consequently, significant differences may be observed by chance alone and p-values should be interpreted as exploratory and with caution.

Details will be described in the statistical epidemiological analysis plan (SAP).

No formal hypothesis testing will be performed since this is a self-controlled study.

All patients who have received at least one dose of Spiolto® Respimat® will be included in the analysis; this is the treated set. All analyses will be performed on the treated set (as-treated analysis). If patients have missing values for an outcome, those patients will be excluded for that outcome's analysis.

The assessment will be carried out using SAS® software, 9.4 version or later. The statistical characteristics presented in the end-of-text tables will be N / mean / SD / min / median / max

for continuous variables. Tabulations of relative and absolute frequencies will be presented for categorical variables. Incidence rates and 95% CI will be given when appropriate.

The analyses will relate to the following data as recorded in the eCRF:

- Patient demographics (age, gender, height, and weight);
- Comorbidities;
- COPD related and other concomitant medication
- History of smoking
- Reported exacerbations
- Breathlessness based on mMRC score at visit 1
- Physical Functioning based on PF-10 scores (therapeutic success at visit 2); primary outcome
- Changes from visit 1 to visit 2 in the PF-10 score; secondary outcome
- Patient satisfaction with Spiolto® Respimat® at visit 2 only; secondary outcome
- General condition of the patient: evaluated by the physician (Physician's Global Evaluation (PGE)); secondary outcome

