3. STUDY OBJECTIVES

3.1. PRIMARY OBJECTIVE

The primary objective of the study is to measure changes in physical functioning - serving as a surrogate for physical activity and exercise capacity - in COPD patients being treated with Spiolto® Respimat® after approximately 6 weeks.

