5.2.3. Analysis of primary endpoint

For the primary endpoint, the proportion of patients with therapeutic success at visit 2 i.e., approximately 6 weeks (define as 10-point increase in the PF-10 score between visit 1 and visit 2) together with the 95% confidence interval will be presented.

***PF-10** is a sub-domain of SF-36 and consists of 10 items evaluating the scope of the restrictions experienced when carrying out routine activities. Each PF-10 item may be answered with “yes, limited a lot”, “yes, limited a little”, or “no, not limited at all”, with a score of 1, 2 or 3. The scores of the 10 items are added up, resulting in a value between 10 (a patient who answers all questions with “yes, limited a lot”) and 30 (a patient who answers all questions with “no, not limited at all”). The final sum of the individual scores will be standardised to a range of 0 to 100 using the following formula: $100 \times (\text{sum} - 10) / 20$.¹

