6. PLANNED ANALYSIS

6.1. STUDY POPULATION

6.1.1. Recruited and assessable patients

According to the section 5.2.2, three populations will be used for the analysis: All screened patients, Treated Set (TS) and Full Analysis Set (FAS). Details of patients excluded from the TS and patients excluded from the FAS will be included in Annex 2, section 8.2.

The important protocol violations will be described in the following table:

Table 1. Important protocol violations-All screened patients		
	n	%
Total patients		100.0
Total with violation of informed consent (IC-1)		
Total with violation of any other inclusion criterion		
Total with violation of any exclusion criterion		
Total with violation of any inclusion or exclusion criterion		

The inclusion criteria and exclusion criteria based on all screened patients according to CRFs:

Table 2. Inclusion and Exclusion criteria-All screened patients		
	n	%
Total patients at screen		
Inclusion criteria not fulfilled		
IC1. Written informed consent prior to participation		
IC2. Female and male patients ≥ 40 years of age		
IC3. Patients diagnosed with COPD and requiring dual bronchodilator (LAMA + LABA) treatment according to approved Spiolto® Respimat® SmPC and GOLD guideline recommendation		
Exclusion criteria fulfilled		
EC1. Patients with contraindications according to Spiolto® Respimat® SmPC		
EC2. Patients who have been treated with a LABA/LAMA combination (free and fixed dose) in the previous 6 months		
EC3. Patients continuing LABA/ICS treatment should not be additionally treated with Spiolto® Respimat® in order to avoid a double dosing of long-acting beta-agonists		
EC4. Patients for whom further follow-up is not possible at the enrolling site during the planned study period of approx. 6 weeks		
EC5. Pregnancy and lactation		
EC6. Patients currently listing for lung transplantation		

Table 2. Inclusion and Exclusion criteria-All screened patients		
	n	%
EC7. Current participation in any clinical trial or any other non-interventional study of a drug or device		

The disposition of patient will be described in the following table:

Table 3. Disposition of patients-All screened patients		
	n	%
Total patients at screen		
Total patients at visit 1		
Total patients at visit 2		
Total patients on Reason for not performing visit 2		
Adverse event		
Serious adverse event		
Patient's wish		
Withdrawn consent		
Lost to follow-up		
Patient died		
Other		
Total patients for discontinuation		
Lost to follow-up		

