6.3.2. Treatment for COPD

This section will describe the continuity of the treatment received for COPD started at the baseline visit and the change in concomitant medication for COPD.

Table 17. Continuation of treatment with Spiolto® Respimat® after 6 weeks (visit 2) - Treated Set (TS)		Total n (%)
Is the patient continuing to receive the treatment with Spiolto® Respimat® started at the baseline visit?		
Yes		
No		
Reason why the patient is no longer receiving Spiolto® Respimat®¹		
Reason 1		
Reason ...		
Has the concomitant medication for COPD changed with respect to the last visit or is the patient receiving a new medication?		
Yes		
SABA		
ICS		
No		

¹ If the patient is no longer receiving the treatment with Spiolto® Respimat® started at the baseline visit (n=xx)

The ANNEX 6. CURRENT TREATMENT FOR COPD 6 will specify the new concomitant medication prescribed for COPD and its duration.

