6.4.1. Analysis of primary endpoint

This section will describe the frequency and percentage of "Therapeutic success" at visit 2 (defined as: 10-point increase in the PF-10 score between the baseline visit (visit 1) and the visit after 6 weeks (visit 2) will be presented together with the 95% confidence interval.

Table 21. Therapeutic success after 6 weeks (visit 2) – Full Analysis Set (FAS)		
	Total n (%)	CI (95%)
Therapeutic success¹ n (%)		
Therapeutically successful		
Not therapeutically successful		

Therapeutic success: 10-point increase in the PF-10 score between visit 1 and visit 2.

¹ Of the total number of patients who have PF-10 data at the baseline visit (visit 1) and at the visit after 6 weeks (visit 2)

Figure 4. Therapeutic success after 6 weeks (visit 2) – Full Analysis Set (FAS)
[pie chart]

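### The primary success rate is a complete-case rate that pools patients on and off Spiolto; a supportive Treated Set row and a split by treatment status would show what it leaves out

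*SAP*

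**What the plan says.** The SAP states the primary objective in section 3.1 as measuring changes in physical functioning "in COPD patients being treated with Spiolto® Respimat® after approximately 6 weeks". The primary endpoint in section 5.2.3 is therapeutic success ("define as 10-point increase in the PF-10 score between visit 1 and visit 2"). It carries no condition on treatment status.

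The FAS (SAP 5.2.2) is "All screened patients with at least one documented administration of Spiolto® Respimat® and available PF-10 score at visit 1 and visit 2". SAP Table 5 assigns the primary endpoint to this set alone. The Table 21 footnote gives the matching denominator: it begins "Of the total number of patients who have PF-10 data at the baseline visit" and goes on to require visit 2 data as well. SAP 5.2.8 allows imputation of missing PF-10 items when fewer than half are missing, and no other imputation.

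Protocol 9.7.1 says "All analyses will be performed on the treated set (as-treated analysis" and then adds: "If patients have missing values for an outcome, those patients will be excluded for that outcome's analysis".

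The information on who is lost and who stops is collected. SAP Table 3 has a block headed "Total patients on Reason for not performing visit 2", with adverse event, death and loss to follow-up among the reasons. Table 17 asks "Is the patient continuing to receive the treatment with Spiolto® Respimat® started at the baseline visit". The visit flow chart in Protocol 9.2.3 collects the reason for stopping Spiolto at visit 2, so a patient who has stopped can still attend and be scored. None of these tables is linked to Table 21.

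**The concern.** In a single-arm descriptive study, one proportion with its confidence interval is the headline result, so the reader needs to know which patients it covers. Two groups are handled without comment.

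- **Treated patients without a PF-10 at both visits** drop out of the denominator. If they do worse than those who return, the reported rate is higher than the rate among everyone who started the drug.
- **Patients who stopped Spiolto but have a visit 2 score** are counted on their score alone. Neither document says how a score obtained after stopping is to be read, and no split by treatment status is planned.

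At stake is the reading of the headline figure. The planned interval reflects sampling error among returners only, and no supportive analysis shows how far the answer depends on those who did not return.

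**Working it through.** **Inputs.** From SAP 4.2 and Protocol 9.5: assumed success rate 50%, 900 evaluable patients, 10% drop-out, 1000 patients in total, stated accuracy ±3.3 points. I take all 1000 as treated and all 100 drop-outs as lacking a PF-10 at one or both visits. The documents give no success rate for drop-outs and no share of patients off Spiolto at visit 2; values for these are assumptions, shown as ranges.

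**1. The plan's own figure.** Normal approximation: p ± 1.96 × √(p(1 − p)/n). With p = 0.50 and n = 900, the half-width is 1.96 × √(0.25/900) = 3.27 points, giving 46.7% to 53.3%. The exact binomial and Wilson intervals round to the same limits. Sample size: 900/(1 − 0.10) = 1000. Both figures reproduce.

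**2. Patients without a score.** With 450 successes among 900 and 100 patients unscored, the all-treated rate is (450 + 100r)/1000, where r is the success rate among the unscored.

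| Assumption about the 100 | All-treated rate | 95% CI |
|---|---|---|
| None successful (r = 0) | 450/1000 = 45.0% | 41.9 to 48.1 |
| r = 20% | 470/1000 = 47.0% | – |
| r = 40% | 490/1000 = 49.0% | – |
| Same as returners (r = 50%) | 500/1000 = 50.0% | – |
| All successful (r = 100%) | 550/1000 = 55.0% | 51.9 to 58.1 |

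The extreme shift is 5 points either way, against a stated ±3.3. The rate falls below 46.7% only if 450 + 100r < 467, that is, r below 17%. By symmetry it rises above 53.3% only if r exceeds 83%.

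If the loss were 5% or 20% of 1000 (assumed), with 50% success among those scored, the bounds would be 47.5% to 52.5% or 40% to 60%.

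**3. Patients off Spiolto at visit 2.** Let a share q of the 900 have stopped, with success rate s among them (both assumed), and hold the pooled rate at 450/900. The on-treatment rate is (450 − 900qs)/(900 − 900q).

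| q | s = 0% | s = 50% |
|---|---|---|
| 2% | 450/882 = 51.0% | 441/882 = 50.0% |
| 5% | 450/855 = 52.6% | 427.5/855 = 50.0% |
| 10% | 450/810 = 55.6% | 405/810 = 50.0% |

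If patients who stopped do worse, pooling them lowers the reported rate relative to an on-treatment rate. This runs opposite to step 2 when non-returners also do worse, so the net direction cannot be stated in advance.

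**4. SAP against protocol.** The protocol starts from the treated set and removes patients with a missing outcome. The SAP defines a set with a PF-10 at both visits. For the primary endpoint the same patients remain under either wording.

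**The case against.** The plan is open about most of this. The Table 21 footnote states the denominator. Tables 3, 4, 16 and 17, the patient flow chart and Annex 2 report losses, reasons and each exclusion from the FAS. The 10% loss is planned for and the analysis is declared descriptive and exploratory. A reader could divide the Table 21 numerator by the Treated Set count. Keeping patients who stopped is also a recognised approach, reporting the outcome whatever happened to treatment. Most of this stands and keeps the point modest. What remains is that the plan itself offers no all-treated figure with an interval, and that Table 21 cannot be separated by treatment status from the planned output.

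Three stronger readings are tempting, and the documents do not support them.

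- *The rate fails to answer the objective.* The objective is to measure change in physical functioning; success belongs to the endpoint. The FAS rate does estimate success among treated patients scored at both visits.
- *The SAP departs from the protocol by leaving the treated set.* The protocol's own exclusion rule leads to the same primary rate (step 4).
- *Success should require still being on Spiolto, among all treated.* This redefines the endpoint, calls a measured 10-point gain a failure, and merges missing data with stopping. With 2% to 10% of the 900 off drug and half of those successful (assumed), it gives (450 − 9)/1000 = 44.1% to (450 − 45)/1000 = 40.5%, and a reader could not tell which component caused the fall.

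**Conclusion.** The point holds as a worthwhile, inexpensive improvement. The primary rate is valid for patients with a PF-10 at both visits, but it may overstate success among all who started Spiolto if those who do not return do worse. The 45.0% to 55.0% range gives bounds rather than an estimate. The 45.0% end assumes that no drop-out improved, and under the assumed 20% to 40% drop-out success the result stays within the plan's stated accuracy. A reader might infer that both features inflate the rate; that is not shown, because patients who stopped may pull it down relative to an on-treatment rate. The sizes rest on the planning figures, on all 1000 patients being treated, and on all drop-outs lacking a score.

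**What to change.** 1. Keep Table 21 on the FAS as the primary result, labelled 'among patients with PF-10 at both visits'.
2. Add one supportive row on the Treated Set, with its 95% CI, in which a patient lacking a PF-10 score at visit 1, visit 2 or both counts as not successful. State that this row is an exception to the no-imputation rule in SAP 5.2.8 (and the same rule in Protocol 9.7.1), and that it is a conservative lower bound.
3. Separately, show Table 21 split by the Table 17 answer on whether the patient was still receiving Spiolto at visit 2. Leave the definition of success unchanged.

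The cost is a little more tabulation and a few sentences in the SAP. All the data are already collected, and no visit or treatment changes. The downside is a second figure that can only be equal to or less favourable than the first, which is why it needs the lower-bound label.

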9.3.2.2 Secondary outcomes

- Changes in the PF-10 score from visit 1 to visit 2
- General condition of the patient, evaluated by the physician (PGE score) at visit 1 and visit 2.
- Patient satisfaction with Spiolto® Respimat® at visit 2.

The following parameters will be collected and assessed at visit 1 and/or visit 2:

- Patient demographics (age, gender, height & weight),
- Smoking status (current smokers, former smokers, and never smokers) and pack-years,
- Concomitant diseases / Comorbidities such as cardiovascular disease, diabetes mellitus, musculoskeletal impairment, renal diseases, liver diseases, osteoporosis, gastroesophageal reflux (GERD), or lung cancer,
- COPD related and other relevant concomitant medication such as beta-blockers, beta-agonists, corticosteroids, or proton pump inhibitors,
- Reported exacerbations based on medical history in the last 12 months and exacerbations leading to hospitalization in the last 12 months,
- Assessment of the severity of breathlessness based on the Modified Medical Research Council Questionnaire (mMRC),
- Physical Functioning based on PF-10 scores*,
- Patient satisfaction with Spiolto® Respimat® to assess the overall satisfaction with Spiolto® Respimat® as well as specific inhalation from the device and device handling,
- General condition of patient based on Physician’s Global Evaluation (PGE) to assess the general condition of the patient at the beginning and at the end of the study,
- Safety Reporting; Adverse Drug Reactions (serious and non-serious), fatal AEs, and pregnancies at the beginning and at the end of the study, as well as,
- GOLD spirometric classifications (1, 2, 3, 4) and GOLD patient groups (A, B, C, D) based on GOLD guidelines

*The PF-10 is a sub-domain of the SF-36 and consists of 10 questions evaluating the extent of experienced restrictions while conducting usual activities. Each question of the PF-10 can be answered with “yes, limited a lot”, “yes, limited a little”, or “No, not limited at all”, with a score of 1, 2, or 3. The scores over the 10 questions will be summed, resulting in a value between 10 (a patient answering all questions with “yes, limited a lot”) and 30 (a patient answering all questions with “No, not limited at all”). The final sum of the individual scores will be standardized to a range of 0 to 100 using the following formula: $100 * (\text{sum-10}) / 20$.

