5.2.8. Handling of missing data

In context of PF-10 questionnaire, if less than half of the items on the PF-10 for a patient are missing, the missing values will be replaced with the mean of the other values and the PF-10 score will be calculated. If half or more of the items on the PF-10 are missing, no score will be calculated and the PF-10 score will be marked as not available.

No other missing data will be imputed. If patients have missing values for any other endpoints, these patients will be excluded from the analysis of that endpoint.

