6.2. DESCRIPTION OF THE SAMPLE AT BASELINE VISIT (VISIT 1, TS)

This section will describe the socio-demographic characteristics, anthropometric data, smoking history and baseline characteristics in terms of the COPD diagnosis, exacerbations, lung function, concomitant diseases, concomitant medication, and previous and current treatment for COPD of the **Treated Set (TS)** (n=xxx) (see *Table 4*).

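### The SAP ties PGE and satisfaction to having a PF-10 score at both visits, whereas the protocol analyses each outcome on the treated patients who have it

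*SAP*

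**What the plan says.** Protocol 9.7.1 defines the treated set as all patients with at least one dose and states: "All analyses will be performed on the treated set (as-treated analysis". It handles missing data outcome by outcome: "If patients have missing values for an outcome, those patients will be excluded for that outcome's analysis".

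SAP 5.2.2 keeps a Treated Set but adds a Full Analysis Set (FAS), made up of screened patients with "at least one documented administration of Spiolto® Respimat® and available PF-10 score at visit 1 and visit 2". On its use, the SAP says: "This population will be used in the primary and secondary tables". Table 5 repeats this allocation, marking the FAS for primary and secondary endpoints and the Treated Set for baseline, 6-week description and safety. Section 6.4 and the titles of Table 24 (PGE) and Table 25 (satisfaction) also name the FAS. Those two titles add a restriction to completed patients, which 5.2.2 does not define as a set.

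PGE and satisfaction are secondary in both documents (protocol 9.3.2.2, SAP 5.2.4). The protocol's PGE entry reads: "General condition of the patient, evaluated by the physician (PGE score) at visit 1 and visit 2".

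On missing data, SAP 5.2.8 says of the PF-10: "If half or more of the items on the PF-10 are missing, no score will be calculated". For everything else it says: "If patients have missing values for any other endpoints, these patients will be excluded from the analysis of that endpoint".

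**The concern.** The PF-10 decides who enters the FAS, but Tables 24 and 25 report other instruments. The PGE is scored by the physician directly in the eCRF (protocol Annex 3). The PF-10 is a paper form completed by the patient (protocol 9.10.2). A complete PGE or satisfaction record can therefore sit beside a PF-10 that cannot be scored. A patient who left five or more PF-10 items blank at visit 1 would lose all three satisfaction answers given at visit 2.

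At stake are two of the three secondary outcomes, reported on a population the protocol did not specify and without valid responses already in the database. Satisfaction includes the item on handling the inhaler, and handling is part of the study title.

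**Working it through.** **1. Which endpoints change set.**

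| Endpoint | Protocol 9.7.1 | SAP 5.2.2, Table 5, section 6.4 | Same patients? |
|---|---|---|---|
| Therapeutic success | Treated, PF-10 at both visits (needed to compute it) | FAS | Yes |
| PF-10 change | Treated, PF-10 at both visits | FAS | Yes |
| PGE, visit 1 versus visit 2 | Treated, PGE at both visits | FAS, then PGE available | No |
| Satisfaction, visit 2 | Treated, satisfaction available | FAS, then satisfaction available | No |

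The per-endpoint rule in SAP 5.2.8 does not close the gap. It removes further patients from a table already limited to the FAS and cannot bring back anyone the FAS has excluded.

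**2. The plan's own precision figure.** Protocol 9.5 and SAP 4.2 assume 50% success in 900 patients. The Wald half-width is 1.96 × √(0.5 × 0.5 / 900) = 0.0327, giving 46.73% to 53.27%. The exact binomial interval is 46.68% to 53.32%. Both round to the stated 46.7% to 53.3%. The drop-out adjustment is 900 / (1 − 0.10) = 1000, as stated. The sample size is not in question.

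**3. Size of the effect at visit 2.** The documents give no rate of unusable PF-10 forms, so three inputs are assumptions:
- 900 visit 2 attenders with the PGE or satisfaction data in question;
- a share u of them, 1%, 2% or 5%, without a usable PF-10 score at one visit or the other;
- a 20-percentage-point difference in the reported proportion between patients kept and patients dropped.

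Formulas: patients dropped = 900u; n kept = 900(1 − u); half-width at 50% = 1.96 × √(0.25 / n kept). The reported proportion minus the all-available proportion = u × 20 points in absolute size, because the all-available figure is (1 − u) × kept + u × dropped.

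| u | Dropped | n kept | Half-width at 50% (points) | Shift (points) |
|---|---|---|---|---|
| 0 | 0 | 900 | 3.27 | 0 |
| 1% | 9 | 891 | 3.28 | 0.2 |
| 2% | 18 | 882 | 3.30 | 0.4 |
| 5% | 45 | 855 | 3.35 | 1.0 |

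Example at u = 2%, with 80% satisfied among those kept and 60% among those dropped: 0.98 × 80 + 0.02 × 60 = 79.6%, so the FAS figure is 0.4 point too high. If the groups do not differ, the shift is zero. Nothing in the documents says which way any difference would run.

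**The case against.** The best defence is that the matter is small and open to view. The study is descriptive, with no confirmatory testing. The FAS is defined plainly, Table 4 gives counts by set, and Table 52 lists each patient outside the FAS with the reason. Replacing items when fewer than half are missing, together with the eCRF completeness checks, should keep unscorable forms rare. All of this stands and limits the size of the point. It does not remove the conflict, because Table 52 shows why a patient is outside the FAS and not what that patient answered on PGE or satisfaction.

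It may also be said that the protocol leaves details to the SAP. It does, but the same section fixes the set for all analyses, so replacing that set is a change that needs to be declared.

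Three stronger readings are tempting and are not supported:

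- *Visit 1 PGE of every treated patient without a visit 2 is wrongly discarded.* This requires reading PGE as two single-visit outcomes. The protocol lists it as one outcome covering both visits, and Table 24 is a before-and-after table with a paired test. Under the protocol's own rule, a patient without visit 2 may properly be excluded.
- *PGE and satisfaction appear nowhere on the Treated Set.* SAP section 5.2.6 and Tables 34 to 47 are not in the public text, so this cannot be confirmed. The FAS assignment itself is in visible text.
- *The primary result is also affected.* It is not. For the two PF-10 endpoints the FAS is exactly the set that outcome-by-outcome exclusion produces, so the success rate needs no extra bounds on this account.

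**Conclusion.** The conflict between protocol 9.7.1 and SAP 5.2.2 is real for visit 2 satisfaction and for the paired PGE comparison. It is stated consistently in 5.2.2, Table 5, section 6.4 and Tables 24 and 25, so it is not a slip in one line. The likely numerical effect is slight: at most 45 patients, 0.08 point of half-width (3.35 − 3.27) and 1.0 point of shift across the range examined. Those figures rest wholly on the assumed 900 attenders, the assumed 1% to 5% without a usable PF-10 pair and the assumed 20-point difference. The case for correcting it is that the SAP departs from the protocol without saying so and omits valid responses to no benefit.

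**What to change.** Amend SAP 5.2.2, Table 5, section 6.4 and Tables 24 and 25 as follows:

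- Satisfaction: Treated Set patients with satisfaction available.
- PGE comparison and its paired test: Treated Set patients with PGE at both visits.
- Therapeutic success and PF-10 change: leave on the FAS.
- Print n for each endpoint, and define or delete the completed-patients wording in the two table titles.

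If the sponsor prefers to keep the FAS for these endpoints, the SAP should at least declare the departure from protocol 9.7.1 and give a reason.

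The cost is SAP wording and printed n values, with no new data. The drawback is that n will differ between endpoints, so the tables no longer share one denominator.

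As a suggestion only, visit 1 PGE could also be described for all treated patients. The Treated Set baseline description in SAP 6.2, whose list ends with "lung function, concomitant diseases, concomitant medication, and previous and current treatment for COPD of the" Treated Set, does not include it. The protocol does not clearly require this, and the tables that are not visible may already cover it.
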